9.3 Efficacy Assessments

Efficacy comparisons will be made in the ITT Population with the intent of estimating the effect of the RD-X19 device relative to sham in several outcome measures. Subjects will be instructed to fill out diary cards twice daily to assess their symptoms associated with disease progression and record the number of treatments completed. Additionally, at Baseline and days 3, 5, and 8, subjects will provide two saliva specimens and an oropharyngeal swab for virology endpoint assessments. One saliva specimen will be collected, preserved, and shipped fresh to a central lab for assessment of SARS-CoV-2 mRNA via RT-qPCR. The second specimen and the oropharyngeal swab will be collected in separate collection tubes, frozen, and stored at the site and shipped to a central lab at the end of each cohort.

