10.4 Statistical Analyses

For continuous variables, descriptive summaries will display number of subjects, arithmetic mean, geometric mean (as appropriate), standard deviation, median, minimum, and maximum by treatment group. For categorical variables, counts and percentages will be displayed.

In general, missing data will not be imputed with the exception that for the ITT analysis, missing viral load results will be imputed using the last-observation-carried-forward (LOCF) methodology.

Additional details regarding statistical methods will be provided in the Statistical Analysis Plan.

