5.2 Handling of Missing Data

5.2.1 Missing Efficacy Endpoints

Missing data will be replaced for the efficacy endpoint in the ITT analyses using the Last observation carried forward (LOCF) method.

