5.5.2 Analysis of Secondary Efficacy Endpoints

The following 6 secondary efficacy endpoints will be summarized using descriptive statistics by visit, as appropriate:

- log10-transformed Viral load as measured in saliva by RT-qPCR at each visit by RT-qPCR
- proportion of subjects with $\geq 95\%$ reduction in SARS-CoV-2 viral load by RT-qPCR at each visit
- time to clearance of viral infection in saliva via RT-qPCR
- proportion of subjects demonstrating clearance of viral infection via RT-qPCR at Day 8/ET visit
- COVID-19 composite severity score at each visit
- time to alleviation of COVID-19 symptoms, defined as the number of hours from the first dose to the first time when all eight symptoms had been assessed by the subject as none (0) or mild (1)
- time to sustained alleviation of COVID-19 symptoms, defined the number of hours from the first dose to the time when all eight symptoms had been assessed by the subject as none (0) or mild (1) and no single symptom reoccurs later at a level above mild (1).

Both time to alleviation of COVID-19 symptoms and time to sustained alleviation of COVID-19 symptoms will be derived from self-assessment by study subjects and recorded on the subjects' diary cards.

For log10-transformed viral load data, geometric means will be computed by exponentiating (base 10) the group means of the log10-transformed viral load. Time-to-event variables will be evaluated using the Kaplan-Meier method and p-values for treatment comparison will be provided via log rank test.

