	n (%) Censored	XX (XX.X)	XX (XX.X)	XX (XX.X)
	Median of Time	XX.X	XX.X	XX.X
	25 th , 75 th Percentiles	XX.X, XX.X	XX.X, XX.X	XX.X, XX.X
	95% CI of Median	(XX.X, XX.X)	(XX.X, XX.X)	(XX.X, XX.X)
	P-value RX-X19 vs. Sham	0.XXX	0.XXX	
Per-Protocol	N	XX	XX	XX
	n (%) Censored	XX (XX.X)	XX (XX.X)	XX (XX.X)
	Median of Time	XX.X	XX.X	XX.X
	25 th , 75 th Percentiles	XX.X, XX.X	XX.X, XX.X	XX.X, XX.X
	95% CI of Median	(XX.X, XX.X)	(XX.X, XX.X)	(XX.X, XX.X)
	P-value RX-X19 vs. Sham	0.XXX	0.XXX	

Abbreviation: CI = Confidence Interval

Note 1: Alleviation of COVID-19 symptoms is defined as all eight symptoms assessed by the subject as none (0) or mild (1).

Note 2: Time to alleviation is calculated as the number of hours from the first dose to the time of the first occurrence of symptoms alleviation. Subjects who did not achieve alleviation at the last assessment of study are considered censored at the time of the last assessment.

Note 3: Percentiles and 95% CI of median are derived using the Kaplan-Meier method. P-values for treatment comparison are from Log Rank Test.

Source: Listing 16.2.6.1.2, 16.2.5.3

O:\Studies\EmitBio\EB-P12-01\Biometrics\Programs\Tables\xxx.sas ran on Month Day, Year at hh:mm on data from Month Day, Year.

Figure 15.2.1 - Kaplan-Meier Plot of Time to Alleviation of COVID-19 Symptoms for Intent-to-Treat Population

Figure 15.2.2 - Kaplan-Meier Plot of Time to Alleviation of COVID-19 Symptoms for Per-Protocol Population

Table 14.2.5.2 – Time to Sustained Alleviation of COVID-19 Symptoms

Population	Statistics	4 Days RD-X19	7 Days RD-X19	Sham
Intent-to-Treat	N	XX	XX	XX
	n (%) Censored	XX (XX.X)	XX (XX.X)	XX (XX.X)
	Median of Time	XX.X	XX.X	XX.X
	25 th , 75 th Percentiles	XX.X, XX.X	XX.X, XX.X	XX.X, XX.X
	95% CI of Median	(XX.X, XX.X)	(XX.X, XX.X)	(XX.X, XX.X)
	P-value RX-X19 vs. Sham	0.XXX	0.XXX	
Per-Protocol	N	XX	XX	XX
	n (%) Censored	XX (XX.X)	XX (XX.X)	XX (XX.X)
	Median of Time	XX.X	XX.X	XX.X
	25 th , 75 th Percentiles	XX.X, XX.X	XX.X, XX.X	XX.X, XX.X
	95% CI of Median	(XX.X, XX.X)	(XX.X, XX.X)	(XX.X, XX.X)
	P-value RX-X19 vs. Sham	0.XXX	0.XXX	

Abbreviation: CI = Confidence Interval

Note 1: Sustained alleviation of COVID-19 symptoms is defined as all eight symptoms assessed by the subject as none (0) or mild (1) AND no single symptom reoccurs later at a level above mild (1).

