Note 2: Time to sustained alleviation is calculated as the number of hours from the first dose to the time of the occurrence of sustained symptoms alleviation. Subjects who did not

achieve sustained alleviation at the last assessment of the study are considered censored at the time of the last assessment.

Note 3: Percentiles and 95% CI of median are derived using the Kaplan-Meier method. P-values for treatment comparison are from Log Rank Test.

Source: Listing 16.2.6.1.2, 16.2.5.3

O:\Studies\EmitBio\EB-P12-01\Biometrics\Programs\Tables\xxx.sas ran on Month Day, Year at hh:mm on data from Month Day, Year.

Figure 15.3.1 - Kaplan-Meier Plot of Time to Sustained Alleviation of COVID-19 Symptoms for Intent-to-Treat Population

Figure 15.3.2 - Kaplan-Meier Plot of Time to Sustained Alleviation of COVID-19 Symptoms for Per-Protocol Population

Table 14.3.1.1 - Treatment-Emergent Adverse Events by System Organ Class and Preferred Term for Safety Population

System Organ Class Preferred Term	4 Days RD-X19 (N=XX) n (%)	7 Days RD-X19 (N=XX) n (%)	Sham (N=XX) n (%)
Subjects Reporting at Least One Adverse Event	XX (XX.X)	XX (XX.X)	XX (XX.X)
System Organ Class #1	XX (XX.X)	XX (XX.X)	XX (XX.X)
Preferred Term #1	XX (XX.X)	XX (XX.X)	XX (XX.X)
Preferred Term #2	XX (XX.X)	XX (XX.X)	XX (XX.X)
...			
System Organ Class #2	XX (XX.X)	XX (XX.X)	XX (XX.X)
Preferred Term #1	XX (XX.X)	XX (XX.X)	XX (XX.X)
Preferred Term #2	XX (XX.X)	XX (XX.X)	XX (XX.X)
...			

Counts reflect numbers of subjects reporting one or more TEAE that map to the MedDRA system organ class/preferred term. At each level of summarization (system organ class or preferred term), subjects reporting more than one TEAE are counted only once.

Source: Listing 16.2.7

O:\Studies\EmitBio\EB-P12-01\Biometrics\Programs\Tables\xxx.sas ran on Month Day, Year at hh:mm on data from Month Day, Year.

Table 14.3.1.2 - Treatment-Emergent Adverse Events by System Organ Class, Preferred Term and Severity for Safety Population

System Organ Class Preferred Term	Severity	4 Days RD-X19 (N=XX) n (%)	7 Days RD-X19 (N=XX) n (%)	Sham (N=XX) n (%)
Subjects Reporting at Least One Adverse Event	Mild	XX (XX.X)	XX (XX.X)	XX (XX.X)
	Moderate	XX (XX.X)	XX (XX.X)	XX (XX.X)
	Severe	XX (XX.X)	XX (XX.X)	XX (XX.X)
System Organ Class #1	Mild	XX (XX.X)	XX (XX.X)	XX (XX.X)
	Moderate	XX (XX.X)	XX (XX.X)	XX (XX.X)
	Severe	XX (XX.X)	XX (XX.X)	XX (XX.X)
Preferred Term #1	Mild	XX (XX.X)	XX (XX.X)	XX (XX.X)
	Moderate	XX (XX.X)	XX (XX.X)	XX (XX.X)

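### Sustained symptom alleviation requires no later diary entry, so one all-none/mild entry at the end of a diary counts as a sustained event instead of being censored

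*Combined protocol and SAP*

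**What the plan says.** SAP 5.5.2 lists time to sustained alleviation as a secondary endpoint, measured in hours from first dose. All eight symptoms must be none or mild, and it is required that "no single symptom reoccurs later at a level above mild (1". Note 1 to Table 14.2.5.2 repeats this: "Sustained alleviation of COVID-19 symptoms is defined as all eight symptoms assessed by the subject as none (0) or mild (1) AND no single symptom" may later exceed mild. Note 2 sets the event time: "Time to sustained alleviation is calculated as the number of hours from the first dose to the time of the occurrence of sustained symptoms alleviation". It also sets the censoring rule: those who did not "achieve sustained alleviation at the last assessment of the study are considered censored at the time of the last assessment".

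The symptom times "will be derived from self-assessment by study subjects and recorded on the subjects' diary cards", and protocol 9.3 gives the frequency: "Subjects will be instructed to fill out diary cards twice daily to assess their symptoms".

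No section sets a minimum duration, a number of confirming entries, a minimum follow-up after alleviation, or a rule for diaries that stop early. On missing data, SAP 5.2.1 says "Missing data will be replaced for the efficacy endpoint in the ITT analyses" by LOCF. Protocol 10.4 is narrower: only "missing viral load results will be imputed using the last-observation-carried-forward (LOCF) methodology". The notes to Table 14.2.5.2 do not mention LOCF.

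The analysis is Kaplan-Meier with log-rank p-values in the ITT and PP populations, and the table is part of the Cohort 1 interim package.

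**The concern.** A condition that forbids later recurrence is satisfied automatically when nothing is observed later. The rule therefore cannot tell a subject seen to stay well from one who was not seen again. Two kinds of subject are affected. One completes the diary but reaches all none/mild only at the final entry. The other stops the diary early, just after a first all-none/mild entry. Kaplan-Meier analysis would normally censor the second subject, because persistence was never observed. The plan instead records a success at the moment of stopping, and for that subject time to sustained alleviation equals time to first alleviation.

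At stake is what the endpoint means: some of its events would carry no evidence of persistence. The arms are small at target numbers. One such event is 1/20 = 5 percentage points in an arm of 20, and 1/10 = 10 points in the interim sham arm of 10.

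**Working it through.** The plan attaches no power, event count or effect size to this endpoint, so there is no stated figure to reproduce. The check applies the rule as written.

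**Step 1: what the rule reduces to.** If the last observed entry has any symptom above mild, no earlier entry can qualify and the subject is censored. If the last observed entry is all none/mild, the start of that final run qualifies. Event status therefore depends only on the last observed entry.

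**Step 2: test diaries.** Twice daily over Days 1 to 8 gives 2 × 8 = 16 entries (inferred from the schedule). Entry 6 is the second entry of Day 3.

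| Diary | Rule as written | At least one later all-none/mild entry required |
|---|---|---|
| Only entry all none/mild, then nothing | event at 1 | censored at 1 |
| 15 moderate, last all none/mild | event at 16 | censored at 16 |
| 5 moderate, one all none/mild, diary stops | event at 6 | censored at 6 |
| 5 moderate, 2 all none/mild, moderate to the end | censored at 16 | censored at 16 |
| 5 moderate, all none/mild to the end | event at 6 | event at 6 |

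The first row is possible because fever alone satisfies inclusion criterion 2 and fever is not one of the eight symptoms. It is probably rare.

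**Step 3: does LOCF change this?** If SAP 5.2.1 covers diaries, an all-none/mild last entry is carried forward and the event stands. If protocol 10.4 governs, nothing is imputed and the event also stands.

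**Step 4: illustrative frequency, assumed rates only.** A two-state simulation (16 entries, everyone starting above mild, 10,000 subjects per setting) used per-entry recovery of 0.05, 0.10 or 0.20, relapse of 0.05 or 0.15, and diary drop-out of 0, 0.02 or 0.05.
- Events with no later entry were 6.0% to 10.7% of all events at relapse 0.05, and 14.8% to 19.4% at relapse 0.15.
- Example: with recovery 0.10, relapse 0.15 and drop-out 0.02, the proportion with an event falls from 36.3% to 30.1% when one later entry is required, a loss of (36.3 − 30.1)/36.3 = 17% of events.

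**Step 5: who these subjects are.** In a simpler stationary model, let p be the chance that an entry is above mild and r the correlation between consecutive entries.
- P(last entry all none/mild, previous entry above mild) = p(1−p)(1−r). At p = 0.3 and r = 0 to 0.7 this is 21% to 6% of subjects. Dividing by 1−p gives p(1−r) = 30% to 9% of events.
- Most of these subjects were all none/mild earlier, relapsed, and ended all none/mild. At r = 0 the chance that all 15 earlier entries were above mild is 0.3^15, effectively zero. At r = 0.7 the chance of being first alleviated at entry 16 is 0.3 × 0.79^14 × 0.21 ≈ 0.2% of subjects, where 0.79 = 0.3 + 0.7 × 0.7 is the chance of staying above mild and 0.21 = 1 − 0.79.
- P(last two entries all none/mild) = 0.7(0.7 + 0.3r) = 0.49 + 0.21r, which passes 50% once r exceeds 0.01/0.21 ≈ 0.05. Over nearly the whole range the median is reached before the final entry, so final-entry events do not move it.

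**The case against.** The best case for leaving the plan alone concerns consequence, not wording. This is one secondary endpoint in a hypothesis-generating study whose p-values are declared descriptive, and first alleviation is reported separately. The PP analysis is limited to study completers, which removes study drop-outs, and Listing 16.2.6.1.2 shows every entry, so single-entry events can be traced. All of this stands and keeps the point small. It does not cure the rule: ITT is primary, and a completer who merely stops the diary stays in PP unless that is separately judged a major deviation. Incomplete diaries are not among the SAP's listed examples.

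A reader might infer several stronger things that the documents do not support.
- **The medians are generally shortened.** Final-entry events fall at the latest possible time, where the alternative is censoring at that same time. Only early diary stops can shorten times materially.
- **The 9% to 30% of events are subjects for whom the endpoint collapses to first alleviation.** Step 5 shows that most had an earlier transient, which the rule correctly rejects before moving the event to the last entry.
- **The device is favoured.** Cohort 1 devices are collected at Day 5 and diaries at Day 8, so earlier stopping in the 4-day cohort is conceivable. The documents give no stopping rates by arm, and any direction would be a guess.
- **Each unconfirmed event is false.** Symptoms may well have stayed away; persistence was simply not observed.

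**Conclusion.** The point holds as a defect in a stated rule. An all-none/mild last or only entry is a sustained event under SAP 5.5.2 and the Table 14.2.5.2 notes, and a diary that stops early at its first such entry is scored as an early sustained success. That follows from the text and needs no assumption.

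The size does not follow from the text. The 6% to 19% range depends on assumed recovery, relapse and stopping rates and moves mainly with relapse. Strong correlation between entries as symptoms resolve would favour the low end. The direction of any between-arm bias is unknown. The consequence is inflated event counts and, for early stops, shortened times. The point is minor but worth correcting, because the twice-daily diary already holds what is needed.

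**What to change.** In SAP 5.5.2 and the notes to Table 14.2.5.2:
- Count an event only when the all-none/mild entry is followed by at least one later observed diary entry with all eight symptoms none or mild, and no later value is above mild. The event time remains the first entry of that run.
- Otherwise censor at the last diary entry.
- State that LOCF under SAP 5.2.1 does not apply to this endpoint, so an imputed value cannot serve as confirmation.
- Apply the rule in Table 14.2.5.2, Figures 15.3.1 and 15.3.2, and the interim analysis.

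A longer window, such as 24 hours (the entry plus the next two), suits a sensitivity analysis better than the main rule. The documents give no basis for that threshold, and in the stationary model at p = 0.3 it removes 1 − (0.7 + 0.3r)² of events, or 17% (r = 0.7) to 51% (r = 0).

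The cost is SAP wording and a short derivation, with no new data. Subjects alleviated only at their final entry become censored, including any genuine late responders. The event count falls by the unconfirmed share: 6% to 19% under the simulation's assumed rates, or 9% to 30% in the stationary model at p = 0.3.

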9.3.1 Efficacy assessments

Various endpoints will explore the impact of RD-X19 treatment on the reduction in log10 SARS-CoV-2 viral load and alleviation of symptoms associated with COVID-19. Both the magnitude of reduction as a function of dose as well as time to clearance will be assessed in support of the primary efficacy analysis. Subjects will be instructed to fill out a diary card or electronic equivalent to assess their signs and symptoms of disease twice daily. Each of the eight symptoms will be rated on a scale from none (0) to severe (3).

- Time weighted average change in viral load from baseline by RT-qPCR from Day 1 to Day 8
- Geometric mean viral load as measured in saliva on day 1, 3, 5, and 8 by RT-qPCR
- Proportion of subjects demonstrating viral load reduction $\geq 95\%$ by RT-qPCR (at each visit)
- Time to undetectable viral load in saliva by RT-qPCR.
- Proportion of subjects demonstrating clearance of viral infection, defined as a negative test via RT-qPCR on Day 8/ET.
- Median time to alleviation of symptoms,
 - The time to alleviation of symptoms endpoint, is defined as the time when all eight symptoms (cough, sore throat, nasal congestion, headache, chills/sweats, muscle or joint pain, fatigue, and nausea) had been assessed by the subject as none or mild.
- Change in COVID-19 Severity Score from baseline
 - The COVID-19 Severity Score is defined as the sum of all the individual symptom severity scores divided by the total number of symptoms assessed (8).
- Viral load by viral titer (at each visit)

- The paired oropharyngeal swab and saliva sample from each subject at each visit allows for independent analysis via two different live virus sampling methodologies and also a direct paired sample comparison of the viral load present in the back of the throat versus saliva.

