5.5 Efficacy Variables and Analyses

All efficacy analyses will be performed for both the ITT and PP populations with results in ITT as primary and PP as supportive.

Viral load (log base 10 copies/mL) and cycle threshold (Ct) data that are continuous in nature but may be reported as “undetermined” or “inconclusive” or “<LOQ”. All virology data will be included in the efficacy analysis except the samples with “Inconclusive” viral load quantitation and the samples with an “Undetermined” RNase P (RP) internal control Ct value.

For analysis-qualified samples, results of “undetermined” and “<LOQ” will be handled as follows for data summary purpose:

- For viral load reported as “Undetermined”, value 1 will be used to calculate descriptive statistics. This will support the need for logarithm transformation.
- For viral load reported as “<LOQ”, value 5×10^1 will be used to calculate descriptive statistics.

In conjunction with above handling of the viral data scenarios, for purposes of this protocol, clearance of viral infection is defined as achievement of: [1] RP Ct ≥ 0 , AND [2] Average N1 Ct ≥ 32 or Average N1 Ct = “Undetermined”.

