5.5.1 Analysis of Primary Efficacy Endpoint

The primary efficacy endpoint is defined as time-weighted average (TWA) change in log10-transformed viral load by RT-qPCR from baseline to Day 8, where TWA will be derived using the trapezoidal rule:

$$\frac{\sum_{i=a}^{b-1} \{0.5 \times (Y_i + Y_{i+1}) \times (t_{i+1} - t_i)\}}{(t_b - t_a)}$$

Y_i is the change from baseline in log10-transformed viral load by RT-qPCR at Visit i , t is the actual study day at the specified timepoint, a is the baseline visit at Day 1, and b is the Day 8 visit.

At the final analysis, each dose of the RD-X19 device will be compared to sham using an Analysis of Covariance (ANCOVA) model with baseline viral load on log10 scale as a covariate and treatment group as an independent variable.

An example of SAS code for the analysis is as follows:

```
proc glm data=datain;
  class trt;
  model aval = trt base /ss3;
  estimate '4x RD-X19 vs Sham' trt 1 0 -1;
  estimate '7x RD-X19 vs Sham' trt 0 1 -1;
  lsmeans trt /pdiff stderr cl;
run;
```

where AVAL denotes the variable to be analyzed, BASE denotes the covariate baseline value, and TRT denotes treatment group with values 1 for 4 Days RD-X19, 2 for 7 Days RD-X19, and 3 for Sham.

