O:\Studies\EmitBio\EB-P12-01\Biometrics\Programs\Tables\xxx.sas ran on Month Day, Year at hh:mm on data from Month Day, Year.

Repeat Table 14.2.2.1 for the following:

Table 14.2.2.2 – Log10-Transformed Viral Load via RT-qPCR by Visit for Per-Protocol Population
 (with footnote 1 removed)

Table 14.2.2.3 – Proportion of Subjects with At Least 95% Reduction by Visit in SARS-CoV-2 Viral Load via RT-qPCR

Population	Study Visit	Statistics	4 Days RD-X19	7 Days RD-X19	Sham
Intent-to-Treat	Visit 3 /Day 3	N	XX	XX	XX
		n (%) Subjects with >=95% Reduction	XX (XX.X)	XX (XX.X)	XX (XX.X)
	Visit 4 /Day 5	N	XX	XX	XX
		n (%) Subjects with >=95% Reduction	XX (XX.X)	XX (XX.X)	XX (XX.X)
	Visit 5 /Day 8	N	XX	XX	XX
		n (%) Subjects with >=95% Reduction	XX (XX.X)	XX (XX.X)	XX (XX.X)
Per-Protocol	Visit 3 /Day 3	N	XX	XX	XX
		n (%) Subjects with >=95% Reduction	XX (XX.X)	XX (XX.X)	XX (XX.X)
	Visit 4 /Day 5	N	XX	XX	XX
		n (%) Subjects with >=95% Reduction	XX (XX.X)	XX (XX.X)	XX (XX.X)
	Visit 5 /Day 8	N	XX	XX	XX
		n (%) Subjects with >=95% Reduction	XX (XX.X)	XX (XX.X)	XX (XX.X)

Note: Missing data will be replaced for the efficacy endpoint in the ITT analyses using the Last observation carried forward (LOCF) method.

Source: Listing 16.2.6.3

O:\Studies\EmitBio\EB-P12-01\Biometrics\Programs\Tables\xxx.sas ran on Month Day, Year at hh:mm on data from Month Day, Year.

Table 14.2.3 – Clearance of Viral Infection in Saliva via RT-qPCR

Population	Endpoint	Statistics	4 Days RD-X19	7 Days RD-X19	Sham
Intent-to-Treat	Time to Clearance of Viral Infection	N	XX	XX	XX
		n (%) Censored	XX (XX.X)	XX (XX.X)	XX (XX.X)
		Median of Time	XX.X	XX.X	XX.X
		25 th , 75 th Percentiles	XX.X, XX.X	XX.X, XX.X	XX.X, XX.X
		95% CI of Median	(XX.X, XX.X)	(XX.X, XX.X)	(XX.X, XX.X)
		P-value RX-X19 vs. Sham	0.XXX	0.XXX	
	Subjects Demonstrating Clearance of Viral Infection at Day 8/ET Visit	n (%)	XX (XX.X)	XX (XX.X)	XX (XX.X)
Per-Protocol	Time to Clearance of Viral Infection	N	XX	XX	XX
		n (%) Censored	XX (XX.X)	XX (XX.X)	XX (XX.X)
		Median of Time	XX.X	XX.X	XX.X
		25 th , 75 th Percentiles	XX.X, XX.X	XX.X, XX.X	XX.X, XX.X
		95% CI of Median	(XX.X, XX.X)	(XX.X, XX.X)	(XX.X, XX.X)
		P-value RX-X19 vs. Sham	0.XXX	0.XXX	
	Subjects Demonstrating Clearance of Viral Infection at Day 8/ET Visit	(%)	XX (XX.X)	XX (XX.X)	XX (XX.X)

Abbreviation: CI = Confidence Interval

Subjects with clearance of viral infection at baseline are excluded from the analysis of time-to-clearance of viral infection.

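### The viral clearance comparisons do not adjust for baseline saliva viral load, which leaves them exposed to chance baseline imbalance and may cost the log-rank test some power

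*Combined protocol and SAP*

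**What the plan says.** SAP 5.5 defines clearance as a valid RNase P control together with an average N1 Ct of at least 32 or Undetermined. It is therefore a fixed cut on the saliva RT-qPCR assay that also supplies baseline viral load.

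- **Time to clearance** (SAP 5.5.2): "Time-to-event variables will be evaluated using the Kaplan-Meier method and p-values for treatment comparison will be provided via log rank test". No covariate or stratum is named.
- **Day 8/ET clearance** (SAP 5.5.2, Table 14.2.3): "The following 6 secondary efficacy endpoints will be summarized using descriptive statistics by visit, as appropriate". The table shell gives n (%) per arm, with no test, interval or model.
- **Use of baseline** (Table 14.2.3 footnote): "Subjects with clearance of viral infection at baseline are excluded from the analysis of time-to-clearance of viral infection". The footnote does not extend to the Day 8 proportion.
- **Primary endpoint** (SAP 5.5.1): an ANCOVA "model with baseline viral load on log10 scale as a covariate and treatment group as an independent variable".
- **Availability of baseline** (Protocol 9.3, version 2.0): "at Baseline and days 3, 5, and 8, subjects will provide two saliva specimens and an oropharyngeal swab for virology endpoint assessments". SAP 5.5 then removes some results: "All virology data will be included in the efficacy analysis except the samples with “Inconclusive” viral load quantitation", and samples whose internal control is undetermined.
- **Role of clearance** (Protocol 9.3.1, which is speaking of the primary analysis): "Both the magnitude of reduction as a function of dose as well as time to clearance will be assessed in support of the primary efficacy".
- **Randomisation** (SAP 3.1): stratified by clinical site only.
- **Status of p-values** (SAP 5.1): descriptive, with no multiplicity adjustment.

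**The concern.** How far a subject starts above a fixed cut largely decides when, and whether, that subject falls below it by Day 8. Baseline viral load is therefore prognostic for clearance by construction. The plan acknowledges this in the primary model but not for the clearance endpoints on the same assay.

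Nothing in the randomisation balances baseline viral load, and the arms are small. If one arm happens to start lower, it will appear to clear faster and more often. Time to clearance is offered as support for the primary result, so a reader would be comparing a baseline-adjusted primary analysis with an unadjusted supporting one.

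**Working it through.** **Inputs from the documents.** Allocation is 20 device to 10 sham per cohort: 20 + 10 = 30, and 2 × 30 = 60 (SAP 3.2). The treatment coding in SAP 5.5.1 and Table 14.2.3 use a single sham group, so each final contrast is 20 v 20 (10 + 10 sham). Post-baseline saliva samples are planned on Days 3, 5 and 8. The sample size is one of convenience. No effect size, SD, event count or power figure is stated, so there is no power figure to reproduce. Every virological input below is an assumption.

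**Step 1: chance imbalance.** SE of the baseline mean difference = SD × √(1/n₁ + 1/n₀).

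- 20 v 20: √(1/20 + 1/20) = 0.32 SD. A gap above 0.5 SD (z = 0.5/0.316 = 1.58) occurs in 11% of trials.
- 20 v 10 (a within-cohort contrast, which Table 14.2.3 does not show): √(1/20 + 1/10) = 0.39 SD. A gap above 0.5 SD (z = 1.29) occurs in 20%.
- At an assumed decline of 0.5 log10/day, one SE is 0.32 log10 or 0.6 days (SD 1.0, 20 v 20). It is 1.5 × 0.387 = 0.58 log10 or 1.2 days in the least favourable case (SD 1.5, 20 v 10).

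**Step 2: effect on the clearance results.** Simulation of 20 v 20 with no device effect, 600 trials per setting. Assumed: baseline mean 4 log10 above the cut; decline 0.5 log10/day with between-subject SD 0.3, 0.25 and 0.2 at baseline SD 1.0, 1.5 and 2.0; assay noise 0.5 log10. The subset is trials where the device arm starts at least 0.4 SD lower.

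| Baseline SD | Subset share | Day 8 difference in subset, raw / adjusted (points) | Falsely favours device in subset, log-rank / adjusted Cox | Type I error over all trials, log-rank / Cox |
|---|---|---|---|---|
| 1.0 | 9% | +11 / +1 | 4% / 4% | 3.3% / 5.3% |
| 1.5 | 10% | +14 / +1 | 14% / 3% | 4.8% / 7.5% |
| 2.0 | 11% | +17 / −1 | 13% / 2% | 5.2% / 6.8% |

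The nominal rate in the fourth column is 2.5%. Each subset holds only about 60 trials (0.10 × 600), so the SE of the 14% is √(0.143 × 0.857/60), about 4.5 points. Over all trials the log-rank holds its size.

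With a device effect of 0.25 log10/day, adjustment reduces the variance of the Day 8 risk difference to 0.88, 0.77 and 0.63 of its raw value at SD 1.0, 1.5 and 2.0. The correlation between the time-to-clearance test statistic and baseline imbalance moves from −0.46, −0.60 and −0.72 to between −0.04 and −0.01.

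**Step 3: power for time to clearance.** Second scenario: baseline mean 6 log10, cut at 3, decline 0.5 (SD 0.2) log10/day, noise 0.4, device slope × 1.6, samples 2, 4 and 7 days after the first dose, baseline-clear subjects excluded. Nominal power uses a 5% cut-off. Size-matched power sets each test's cut-off from its own null simulations: run 1 has 2,000 null and 1,000 effect trials per cell, run 2 has 1,500 and 800. Entries are log-rank v adjusted Cox.

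| Contrast, baseline SD | Nominal | Size-matched, run 1 | Size-matched, run 2 |
|---|---|---|---|
| 20 v 20, 0.75 | 67% v 69% | 69% v 64% | 69% v 67% |
| 20 v 20, 1.0 | 57% v 65% | 64% v 69% | 60% v 68% |
| 20 v 20, 1.5 | 48% v 62% | 49% v 55% | 53% v 58% |
| 20 v 10, 0.75 | 49% v 50% | 53% v 51% | 48% v 48% |
| 20 v 10, 1.0 | 42% v 49% | 44% v 48% | 44% v 45% |
| 20 v 10, 1.5 | 33% v 50% | 35% v 42% | 34% v 44% |

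Monte Carlo error is about 1.6 to 1.8 points on each power, plus error in the estimated cut-offs. The size-matched gain is nil at SD 0.75 (−5 to 0 points), 1 to 8 points at SD 1.0 and 5 to 10 points at SD 1.5. The Cox likelihood-ratio test is liberal: its highest type I error was 6.9% to 8.3% across runs of this scenario. At 20 v 20 and SD 1.5 in run 1 it was 8.3%, against 5.1% for the log-rank.

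**The case against.** These are secondary endpoints in a convenience-sized, hypothesis-generating study with descriptive p-values, and Day 8 clearance has no planned between-arm test at all. Chance imbalance is part of the sampling variation that the log-rank p-value already allows for. The plan also handles baseline elsewhere: Table 14.2.2.1 shows it by arm, the primary model adjusts for it, and the endpoint of at least 95% reduction is relative to each subject's own baseline. Entry on a recent positive antigen test and at most 3 days of symptoms may narrow the baseline spread.

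Much of this stands. It limits the stakes, and it rules out inferring that the log-rank is invalid or that false positives are inflated overall. The nominal figures also invite a claim of 14 to 17 points of power at SD 1.5 (48% to 62%, 33% to 50%). Part of that is the Cox test's inflated size, and 5 to 10 points remain once the tests are matched.

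The rest does not remove the point. A baseline table reveals an imbalance but not what it did to clearance. The 95% reduction endpoint answers a different question. Descriptive contrasts still shape the next decision. As for spread, the Table 14.2.3 footnote itself provides for subjects already below the cut at baseline. And because sham is pooled over two cohorts enrolled in sequence, baseline differences need not be due to chance alone.

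**Conclusion.** The point holds as a cheap improvement to secondary analyses; it does not threaten the trial. The harm is conditional bias when one arm starts lower, plus a power loss that ranges from nil to about 10 points. That range rests on the assumed slopes, device effect and cut as well as on a baseline SD that the plan does not give.

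A reader might go further in three ways that the documents do not support:

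- **That any disagreement between clearance and the primary result would come purely from the missing adjustment.** Time-weighted average change and a threshold crossing read at three visits are different quantities and can diverge for other reasons.
- **That adjustment tightens the hazard ratio.** The gain there is in power and conditional bias, and the standard error need not fall. The Day 8 risk difference does gain precision in the simulation.
- **That baseline is available for everyone.** It is planned for everyone; inconclusive or control-failed samples may leave a few subjects without a value.

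**What to change.** In SAP 5.5.2 and Table 14.2.3, before unblinding for the final analysis:

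1. Keep the Kaplan-Meier curves and the log-rank p-value. Beside them, add a Cox model (Efron ties) or a discrete-time complementary log-log model with treatment group and baseline log10 viral load. One covariate is enough: the first simulation produced only about 17 to 23 events per contrast.
2. Take that model's p-value from a permutation test, permuting labels within cohort and site as randomised, because the likelihood-ratio test can be liberal at this size.
3. For Day 8/ET clearance, add a risk difference with 95% CI, standardised over baseline log10 viral load, beside the raw percentages. Say whether subjects already clear at baseline are included. If the SAP 5.5 substitution of 1 for Undetermined carries into the covariate, such a subject enters at log10(1) = 0.
4. State how subjects with no usable baseline sample are handled.

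The cost is SAP wording and one extra model per analysis set, with no new data or visits. The adjusted hazard ratio is a conditional rather than a marginal quantity and should be labelled so.
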